### **5.8.3. Clinical Laboratory Measurements**

Baseline clinical laboratory analytes and change from baseline in clinical laboratory analytes to each scheduled assessment time will be summarized with descriptive statistics for each treatment group.

Listings will be provided with flags indicating the out of laboratory range values.

A treatment-emergent Potential Clinically Significant abnormal value (PCSV) is a laboratory value that was normal or abnormal but not meeting PCSV criteria at Screening and Baseline but became abnormal and met PCSV criteria after treatment with study drug. Definitions of PCSV is listed in Section 10.3. Treatment-Emergent Potentially clinically significant values (PCSVs) will

be summarized by treatment group. The PCSV laboratory summaries will be constructed for both Year 1 and Year 2 On-Treatment Periods.

For hs-CRP and alkaline phosphatase, subgroup analysis will be performed for the following:

- Adjudicated Arthropathy category 1 (Presence of AA: patients without / with AA)
- Adjudicated Arthropathy category 2 (Subtype of AA: patients without AA, patients with RPOA-1, and patients with other AA subtype except RPOA-1)
- Destructive Arthropathy category (Presence of DA: patients without AA, patients with non-DA AA, patients with DA)

For hs-CRP, plots of means and medians of the change from baseline over time will be presented by treatment group.

For alkaline phosphatase, plots of means of the observed change from baseline over time will be presented by treatment group, overall and by subgroup.

Lab data collected during the Pre-Treatment Period will be displayed in listings.

#### **5.8.4. Analysis of Vital Signs**

Vital signs (blood pressure, temperature and respiration rate) will be summarized by baseline and change from baseline to each scheduled assessment time with descriptive statistics.

A treatment-emergent Potential Clinically Significant abnormal value (PCSV) is a vital sign value that was normal or abnormal but not meeting PCSV criteria at Screening and Baseline but became abnormal and met PCSV criteria after treatment with study drug. Definitions of PCSV is listed in Section 10.3. Treatment-Emergent Potentially clinically significant values (PCSVs) will be summarized by treatment group. The PCSV laboratory summaries will be constructed for both Year 1 and Year 2 On-Treatment Periods

The incidence of orthostatic hypotension, separated out by the specific criteria leading to an orthostatic hypotension diagnosis, will also be summarized by treatment group.

The above vital sign summaries will be constructed for the Year 1 and 2, Treatment and Follow-up Periods. Vital sign data collected during the Pre-Treatment Period will be displayed in listings.

#### **5.8.5. Analysis of 12-Lead ECG**

ECG parameters (Ventricular rate, Heart Rate, PR interval, QRS interval, QT interval and QTc interval) will be summarized by baseline and change from baseline to each scheduled assessment time by treatment group.

A treatment-emergent Potential Clinically Significant abnormal value (PCSV) is an ECG value that was normal or abnormal but not meeting PCSV criteria at Screening and Baseline but became abnormal and met PCSV criteria after treatment with study drug. Definitions of PCSV is listed in Section 10.3. Treatment-Emergent Potentially clinically significant values (PCSVs) will be summarized by treatment group.

ECG status (i.e. normal, abnormal) will be reported. Shift tables will be provided to present the post-baseline status according to the baseline status (normal or missing / abnormal) by treatment group.

The above ECG summaries will be presented for both On-Treatment Periods.

#### **5.8.6. Physical and Neurological Examinations**

The percentage of patients with new-onset clinically significant abnormal physical examinations will be summarized by treatment group showing frequency and percentage by body system for each period as well as at the end of the study. Similarly, summaries will be presented for neurological exam findings. These summaries will be constructed for the Treatment and Follow-up Periods, for both Year 1 and 2.

#### **5.8.7. Analysis of Other Safety Variables**

Other safety data includes the survey of Autonomic Symptoms, cases of AA and joint replacements.

##### Survey of Autonomic Symptoms

The number of patients reporting the presence of each symptom/health problem assessed will be presented by treatment group at each scheduled visit. The number of symptoms reported, and total symptom impact score will be presented by treatment group at each scheduled visit.

##### Adjudicated Arthropathy

Adjudicated arthropathy events based on imaging data overall and by subtype will be summarized by treatment group based on the SAF. Time to first AA event will be summarized by Kaplan-Meier method. Cox regression model will be used for descriptively comparing each treatment group to placebo by obtaining hazard ratio estimates along with 95% confidence intervals. Swimmer plots depicting the length of the observation window per patient and indicating timepoints at which the initial event occurred, worsened and/or changed subtype category may be presented by treatment group.

Time to first DA event will be summarized by Kaplan-Meier method. Cox regression model will be used for descriptively comparing each treatment group to placebo by obtaining hazard ratio estimates along with 95% confidence intervals.

All-cause joint replacements of any joint will be summarized by treatment group. The number of replacements in joints that were positively adjudicated will be summarized by treatment group. Joint replacements will also be summarized by KL score of the affected joint at screening.

In the time to event analyses, Time to first event will be calculated as : (Date of the first event – Date of the first dose of study drug +1 ). Patients without an event will be censored at the last visit for AA and DA in the analysis.

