The patients will be stratified by the affected index joint (hip or knee), by Kellgren-Lawrence (K-L) score (2 to 3, or 4), and by geographic region to enable analysis of efficacy and safety (as defined in Section 5.1). The K-L stratification scheme is used here to ensure that there is an equal distribution of patients with the most severe OA at baseline across the dosing groups.

The inclusion of a placebo treatment group in Year 1 is important to accurately determine the efficacy of fasinumab. Non-steroidal anti-inflammatory drugs are the most common medications used to treat pain due to OA. Therefore, comparison of fasinumab to the NSAIDs treatment group will aid in determining the efficacy of fasinumab compared to a frequently used and effective standard of care class of medications for OA, but that have associated clinically significant AEs. As naproxen is a commonly used and highly effective NSAID (Ong 2007), it has been selected as the comparator drug for this study.

Inclusion of both the placebo group and the active treatment comparator group in Year 1 will be important to accurately estimate the risk of AEs, including the AEs of special interest of

adjudicated arthropathy, sympathetic nervous system dysfunction, and altered peripheral sensation. Specific questionnaires and physical examinations will be employed to monitor for these AEs of special interest. All patients included in the study will have regular study visits and receive diagnostic procedures (ie, X-rays, magnetic resonance imaging [MRI]) to evaluate their ongoing OA. Adverse event monitoring will be ongoing throughout the trial. Patients and investigators can choose to end participation at any time.

Acetaminophen/paracetamol will be made available as rescue treatment for any patient as appropriate. Therefore, the use of a placebo group is justified, as placebo-treated patients will not be placed at significant risk.

#### Year 2

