#### **3.1. The Full Analysis Set (FAS)**

The FAS includes all randomized patients excluding patients affected by the urgent safety measure (i.e. patients randomized to the 3 mg Q4W or 6 mg Q8W doses) and is based on the treatment allocated (as randomized). Efficacy and patient reported outcome endpoints for Year 1 will be analyzed using the FAS including patients randomized to fasinumab 1 mg Q4W, fasinumab 1 mg Q8W, naproxen and placebo. For the analyses of fasinumab 1 mg Q8W group comparing to the control groups, only patients concurrently randomized (i.e. after Protocol R475-OA-1611 Amendment 5 Global was implemented) will be included.

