#### **3.2. The Modified Full Analysis Set (mFAS)**

Due to regional irregularities noted in a parallel phase 3 study that became fully apparent only after unblinding that study, and the concern that the same irregularities would be present in data from similar sites from the same region in this study, the primary and secondary efficacy analyses will be performed on a modified Full Analysis Set (mFAS). This mFAS is comprised of the FAS excluding patients from the region of concern (Rest of the World stratum). Efficacy and patient reported outcome endpoints will be analyzed using the mFAS including patients randomized to fasinumab 1 mg Q4W, fasinumab 1 mg Q8W, naproxen and placebo. For the analysis of fasinumab 1 mg Q8W group comparing to the control groups, only the subset of patients concurrently randomized (ie, after Protocol R475-OA-1611 Amendment 5 Global was implemented) will be included.

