#### **3.4. The Safety Analysis Sets (SAF)**

The Year 1 safety analysis set (SAF – Year 1) includes all randomized patients from the FAS who received any study drug; it is based on the treatment received (as treated). Treatment compliance/administration and all clinical safety variables for Year 1 will be analyzed using the

SAF – Year 1 including patients randomized to fasinumab 1 mg Q4W, fasinumab 1 mg Q8W, naproxen, and placebo.

The Year 2 safety analysis set (SAF – Year 2) includes all patients who received at least 1 dose of the Year 2 study drug; it is based on the treatment received during Year 2 (as treated). Treatment compliance/administration, all clinical efficacy and safety variables and all patient reported outcomes from Year 2 will be analyzed using the SAF – Year 2.

The following rules will be used to define the actual treatment a patient received:

- Patients randomized to either the placebo or naproxen arm who receive at least one dose of active fasinumab during Year X will be considered as treated with fasinumab 1 mg Q8W and classified in the fasinumab 1 mg Q8W treatment arm for the purpose of analysis using the SAF – Year X, where X = 1 or 2.
- Patients randomized to the placebo arm who have not received any active fasinumab injections but were ever dispensed active naproxen during Year 1 will be considered as treated with naproxen and classified in the naproxen treatment arm for the purpose of analysis using the SAF – Year 1.
- For patients randomized to either the fasinumab 1 mg Q8W or Q4W arms, as treated is defined to be as randomized and they will be classified in the treatment arm they were randomized to for the purpose of the analysis using the SAF – Year X, where X = 1 or 2, with the following exceptions:
  - In Year 1, if a patient receives no doses of active naproxen or fasinumab, then the patient will be considered as treated with placebo and classified in the placebo treatment arm for the purpose of analysis using the SAF – Year 1.
  - In Year 1, if a patient receives no doses of fasinumab but were ever dispensed any active dose of naproxen, then the patient will be considered as treated with naproxen and classified in the naproxen treatment arm for the purpose of analysis using the SAF – Year 1.
  - In Year 2, if a patient receives no doses of fasinumab, then the patient will be considered as treated with naproxen prn and classified in the naproxen prn treatment arm for the purpose of analysis using the SAF – Year 2.

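### The Q8W-versus-placebo hazard ratios for adjudicated and destructive arthropathy are not limited to concurrently randomized placebo patients

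*SAP*

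**What the plan says.** SAP 5.8.7, under Adjudicated Arthropathy, sets the population: "Adjudicated arthropathy events based on imaging data overall and by subtype will be summarized by treatment group based on the SAF". It then states that a "Cox regression model will be used for descriptively comparing each treatment group to placebo by obtaining hazard ratio estimates", with 95% confidence intervals, and repeats the sentence for DA. It names no covariates, no stratification and no limit on which placebo patients enter. Year 2 has no placebo group, so a contrast with placebo has to use the Year 1 safety set.

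SAP 3.4 defines that set as every treated FAS patient, grouped as treated. It does not mention when patients were randomized. The other sets do:

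- FAS (SAP 3.1), for Q8W against the controls: "only patients concurrently randomized (i.e. after Protocol R475-OA-1611 Amendment 5 Global was implemented) will be included".
- mFAS (SAP 3.2): "only the subset of patients concurrently randomized (ie, after Protocol R475-OA-1611 Amendment 5 Global was implemented) will be included".
- PPS (SAP 3.3): the same restriction again.

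SAP 5.7.1 gives the reason when it sets up the Q8W primary test: the arm was not in the study before Amendment 5, so only later patients are used.

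On the strata, Protocol 3.2.1 says patients are stratified by index joint, K-L score and region "to enable analysis of efficacy and safety", and adds that the K-L factor is there to spread the most severe OA evenly across groups. The primary and key secondary efficacy models carry all three factors.

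**The concern.** Q4W and placebo patients were randomized side by side, 3:1, both before and after Amendment 5. Q8W patients were randomized only after it. If all placebo patients serve as the comparator, the Q4W hazard ratio is a randomized contrast throughout, while the Q8W hazard ratio mixes a randomized contrast with a historical one. Any difference between the two enrolment periods in arthropathy risk, follow-up or detection then passes into the Q8W estimate. The two fasinumab hazard ratios would also rest on differently matched controls, which clouds any reading by dose. Protocol 1.1 reports that AA appeared dose-related in an earlier study and influenced dose selection.

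The periods differ in at least one documented way. Protocol 7.3.2.1 required patients enrolled under earlier versions who met newly excluded conditions to stop study drug.

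**Working it through.** **Inputs from the documents.** Protocol 5.1.3: about 80 placebo patients before Amendment 5; 200 placebo and 600 Q8W planned under it. SAP 2.2: two-sided alpha 0.025, Q8W effect size 0.368, dropout 15% to week 16. These are planned, as-randomized counts; the as-treated safety set will differ a little.

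**Inputs assumed.** The documents give no AA rates, hazard ratios or K-L effect for this study. Ranges used: one-year placebo AA risk 0.5% to 3%, hazard ratio 2 to 4, k from 0.5 to 3, and K-L 4 tripling AA risk.

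**1. The plan's own figure.** The documents state no power or event count for the Cox models. The nearest figure is 97% power for Q8W versus placebo on WOMAC at week 16. With 510 and 170 completers, 0.368 × √(510 × 170/680) = 4.155. Subtracting 2.241 gives 1.914, so power is 97.2%, which reproduces the plan. With all 280 placebo patients it would be 99.3%. The efficacy planning for Q8W therefore rests on the 200 concurrent patients.

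**2. Share of non-concurrent placebo.** 80/280 = 28.6%.

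**3. Effect of pooling.** For rare events with similar follow-up, the pooled placebo hazard relative to the concurrent one is (200 + 80k)/280. The Q8W hazard ratio is multiplied by the inverse, 280/(200 + 80k):

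| k | multiplier |
|---|---|
| 0.5 | 280/240 = 1.17 |
| 1 | 1.00 |
| 1.5 | 280/320 = 0.88 |
| 2 | 280/360 = 0.78 |
| 3 | 280/440 = 0.64 |

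Simulated Cox fits agree (300 trials per scenario, true hazard ratio 2, placebo base risk 3%). The median hazard ratio with pooled placebo was 2.35–2.39 at k = 0.5, 2.03–2.05 at k = 1 and 1.55–1.63 at k = 2. With concurrent placebo it was 1.99–2.15 throughout.

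**4. How much a K-L shift alone could do.** Mean relative risk is 1 + 2p, where p is the K-L 4 share. Stratified randomization gives concurrent placebo essentially the Q8W share.

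- 20% before, 25% after: pooled share (50 + 16)/280 = 23.6%; 1.50/1.471 = 1.02.
- 20% before, 30% after: pooled share (60 + 16)/280 = 27.1%; 1.60/1.543 = 1.04.
- 15% before, 25% after: pooled share (50 + 12)/280 = 22.1%; 1.50/1.443 = 1.04.

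**5. Adding the strata.** In the same simulations, stratifying by K-L with a K-L hazard ratio of 3 moved the median hazard ratio by at most about 0.04 and left the standard error unchanged to within 0.001.

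**6. Cost of restricting.** SE(log HR) = √(1/d1 + 1/d0), where d1 and d0 are the event counts. At 2% placebo risk and hazard ratio 2, d1 = 23.8, and d0 falls from 5.6 to 4.0. The SE rises from 0.470 to 0.540, or 15%. Across the assumed ranges the rise is 15–17%.

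**The case against.** **The safety set may inherit the rule.** It is drawn from the FAS, and the FAS restriction covers Q8W-versus-control analyses without the word efficacy. This is arguable, and the point rests on an omission. But the mFAS and PPS are derived from the FAS too, and both restate the rule. In the FAS definition the sentence also follows text on efficacy and patient-reported endpoints. Two programmers could reasonably build different Q8W comparators.

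**Nothing in the documents points to an arthropathy-related shift.** The Amendment 5 entries do not list the inclusion criterion on OA diagnosis, K-L score and index joint. The newly excluded conditions are cardiovascular, renal and antihypertensive. This stands: k near 1 is quite possible. It is still an assumption that a concurrent comparison does not need.

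**Restriction may cost more than it saves.** A K-L effect of 2–4% is 0.02–0.04 on the log scale, under a tenth of an SE of 0.47. Even at k = 2 the bias is ln 0.778 = −0.25, and √(0.470² + 0.251²) = 0.533, no worse than the restricted SE of 0.540. This also stands and is the reason to keep the pooled estimate. In favour of restriction, imprecision shows in the confidence interval and bias does not.

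**Covariates add little and may destabilise sparse models.** True. With about 4 to 6 placebo AA events at 2% risk, and perhaps fewer DA events, a fallback is needed.

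**Conclusion.** The point holds as a gap in the specification of a descriptive comparison. On the literal text, about 80 of 280 placebo patients in the Q8W AA and DA hazard ratios were never randomized against Q8W, contrary to the SAP's own rule for the same contrast in efficacy. The direction and size of any bias are unknown. The multipliers depend entirely on k, which the documents do not inform, and there is no bias at k = 1. Q4W is not affected.

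Three stronger readings are not supported:

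- **A large bias through K-L mix.** A reader might set the K-L 4 share at 30% in Q8W and 20% in pooled placebo, giving 1.60/1.40 = 1.14. With 60 of the 200 concurrent placebo patients at K-L 4, a pooled 20% (56 of 280) needs (56 − 60)/80 = −5% among the earlier 80, which is impossible. A 25% versus 20% contrast needs (56 − 50)/80 = 7.5% among them, which is possible but extreme.
- **Leaving out the strata distorts the hazard ratios.** It barely moves them. Protocol 3.2.1 describes balance by design and does not promise covariate adjustment.
- **This is the main safety endpoint.** Protocol 4.3.1 lists AA and DA incidence among six unranked safety endpoints, and SAP 4.6.8 places time to AA and DA under exploratory safety endpoints. No test, alpha or decision rule is attached.

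**What to change.** In SAP 5.8.7, state that the Q8W-versus-placebo hazard ratios for AA and DA use only patients randomized after Amendment 5. Stratifying the Cox model by pre- and post-Amendment 5 period would serve equally: the earlier stratum has no Q8W patients, so it adds nothing to that contrast but still informs Q4W. Show the pooled-placebo estimate as supportive.

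As a minor addition, include K-L category and index joint as covariates, with region if events allow, and name an unadjusted fallback for sparse events. Expect little numerical effect.

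The change is a few sentences and needs no new data. The price is about 200 rather than 280 placebo patients in the Q8W contrast, with the 15–17% larger standard error shown above.

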#### **Population**

#### Sample Size:

Enrollment of approximately 2845 patients is planned for this study, which includes a total of 285 patients who were enrolled in the fasinumab 3 mg SC Q4W and 6 mg SC Q8W groups under earlier versions of the protocol before dosing was discontinued due to the urgent safety measure, and a total of approximately 2560 patients who will be randomized to fasinumab 1 mg SC Q4W, 1 mg SC Q8W, naproxen, and placebo.

Approximately 840 patients will be randomized to the fasinumab 1 mg SC Q4W group, 840 patients to the naproxen-only group, and 280 patients to the placebo group. An estimated 600 patients will be randomized to the fasinumab 1 mg Q8W group.

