Data from studies of tanezumab and fulranumab demonstrated these molecules were associated with an increased risk of destructive arthropathy (DA), a unique clinical form of rapidly progressive arthropathy over and above that seen in the normal progression of osteoarthritis. Analyses of the tanezumab data by its sponsor, defined by anatomic pathological criteria on specimens obtained on joint replacement (JR), revealed that the risk of DA increases with tanezumab dose and is further increased with the concomitant use of chronic NSAIDs (>90 days) (Lane 2010). Most cases of DA occurred in joints with a documented history of OA.

Based on the potential risk of DA identified in tanezumab and fulranumab, the US Food and Drug Administration (FDA) placed this class of anti-NGF antibodies on clinical hold in 2010. Following a review of anti-NGF antibody clinical data in March 2012, the FDA determined that clinical studies of anti-NGF therapies could resume if mitigation strategies are implemented to minimize the risk of DA. To address concerns about potential events of DA, a risk-mitigation approach is also being implemented for all fasinumab studies, as outlined in Section 9.6.1.1. This approach includes sensitive, prospective, and rigorous radiologic screening and monitoring for select changes in joint structure. The patients who develop these changes, which are referred to throughout this document as adjudicated arthropathy (AA), are required to discontinue study therapy.

Since the removal of the FDA clinical hold, Regeneron has conducted or initiated several clinical trials of fasinumab. In all clinical studies to date, fasinumab was associated with a low rate of discontinuations due to adverse events. Patients treated with fasinumab generally had more frequent events than did placebo-treated patients of arthralgia, joint swelling, peripheral edema, altered peripheral sensation (eg, paresthesia, dysesthesia), and myalgia.

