**Figure 1: Study Flow Diagram**

Abbreviation: EOS- End of study

Prior to Protocol R475-OA-1611 Amendment 4 Global, patients were randomized 3:3:3:3:1 to receive one of the following treatment regimens:

- Fasinumab 1 mg Q4W - Fasinumab 1 mg SC Q4W and naproxen-matching placebo oral, twice daily
- Fasinumab 3 mg Q4W - Fasinumab 3 mg SC Q4W and naproxen-matching placebo oral, twice daily
- Fasinumab 6 mg Q8W - Fasinumab 6 mg SC Q8W (patients received placebo injections at the study visits where study drug was not administered) and naproxen-matching placebo oral, twice daily

- Naproxen - Fasinumab-matching placebo SC Q4W and naproxen 500 mg oral, twice daily
- Placebo - Fasinumab-matching placebo SC Q4W and naproxen-matching placebo oral, twice daily

A total of 285 patients were enrolled in the fasinumab 3 mg SC Q4W and fasinumab 6 mg SC Q8W groups. However, dosing in these patients was discontinued, as recommended by the independent Data Monitoring Committee (DMC) in April 2018.

Post Protocol R475-OA-1611 Amendment 5 Global approximately 2,560 patients were planned to be randomized 3:3:3:1 to receive:

- Fasinumab 1 mg Q4W - Fasinumab 1 mg SC Q4W and naproxen-matching placebo oral, twice daily
- Fasinumab 1 mg Q8W - Fasinumab 1 mg SC Q8W (patients received placebo injections at the study visits where study drug was not administered) and naproxen-matching placebo oral, twice daily
- Naproxen - Fasinumab-matching placebo SC Q4W and naproxen 500 mg oral, twice daily
- Placebo - Fasinumab-matching placebo SC Q4W and naproxen-matching placebo oral, twice daily

Randomization was stratified according to the affected index joint (hip or knee), the K-L score (2 to 3, or 4) at the screening visit, and geographical region (Europe, North America, and Rest of the World [South Africa]).

Protocol R475-OA-1611 Amendment 6 provided patients the option to continue in the study and receive treatment for an additional year (Year 2). The treatment arm the patients were assigned in Year 2 was determined by the treatment arm they were randomized to in Year 1 according to the following rules:

- Patients randomized to receive Placebo or Naproxen in Year 1 will be assigned to receive Naproxen prn during Year 2
- Patients randomized to received Fasinumab 1 mg Q4W in Year 1 will be assigned to remain on this dose for Year 2
- Patients randomized to received Fasinumab 1 mg Q8W in Year 1 will be assigned to remain on this dose for Year 2

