## 2.2. Sample Size and Power Considerations

In this study, approximately 2560 patients were planned to be randomized to fasinumab 1 mg SC Q4W (840), fasinumab 1 mg SC Q8W (600), naproxen (840), or placebo (280) (see Section 5.1.3 of the protocol). This sample size was expected to provide adequate power for the comparisons between fasinumab and naproxen at week 16 for the WOMAC pain and physical function scores and the Patient Global Assessment - Osteoarthritis (PGA-OA) score and provide long term data for safety assessment.

The sample size was based on results of the WOMAC pain and physical function subscale scores and the PGA from the R475-PN-1227 study. The calculation of sample size assumed a 2-sided alpha level of 0.025 and a 15% dropout rate up to week 16 and a 30% dropout rate up to week 52. Enrollment of 840 patients in the fasinumab 1 mg Q4W group and 280 patients in the placebo group would have provided at least 99% power to detect an effect size of 0.46 in the WOMAC pain and physical function subscale scores (i.e., an absolute treatment difference of 1.1 between fasinumab and placebo and a standard deviation [SD] of 2.4 at week 16 and 52 for the full analysis set [FAS]). This sample size would have provided 99 % power to detect an effect size of 0.36 in PGA for an absolute treatment difference of 0.4 with a SD of 1.1 at week 16, and 98% power at week 52 for the FAS.

For the fasinumab 1 mg Q8W group, the 600 patients would have been compared to the approximately 200 patients in the placebo group who were enrolled after Protocol R475-OA-1611 Amendment 5 Global was implemented. For such comparisons, 2-sided alpha level of 0.025 and a 15% dropout rate up to week 16 and a 30% dropout rate up to week 52 were assumed. Additionally, the effect size for such comparisons were assumed to be 80% of the effect size for the comparison between fasinumab 1 mg Q4W group and the placebo group. Under these assumptions, enrollment of 600 patients in the fasinumab 1 mg Q8W group and 200 patients from the placebo group would have provided 97% power to detect an effect size of 0.368 ( $=0.46*80%$ ) in the WOMAC pain and physical function subscale scores at week 16 and 93% power at week 52. This sample size would have provided 84% power to detect an effect size of 0.288 ( $=0.36*80%$ ) in PGA at week 16, and 75% power at week 52 for the full analysis set (FAS).

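### The destructive-arthropathy hazard ratio versus placebo has no stated interval type and no rule for an arm without events; with no placebo case, the usual Cox estimate and its Wald 95% CI carry no information

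*SAP*

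**What the plan says.** SAP 5.8.7, under Adjudicated Arthropathy, treats adjudicated arthropathy (AA) and DA alike. For DA, "Time to first DA event will be summarized by Kaplan-Meier method", followed by "Cox regression model will be used for descriptively comparing each treatment group to placebo by obtaining hazard ratio estimates along with 95% confidence intervals". On censoring it says "Patients without an event will be censored at the last visit for AA and DA in the analysis". It does not say whether the intervals are Wald, profile-likelihood or exact, and it has no provision for an arm with no events. SAP section 8 names only the SAS version. By contrast, SAP 5.7.1 does give fallback covariance structures in case the efficacy model fails to converge.

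The other DA outputs are descriptive by arm: incidence (SAP 5.8.2), number and percentage of patients (SAP 4.6.8) and the Kaplan-Meier summary. None of them gives a between-arm effect estimate.

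The arm sizes come from the efficacy calculation. The Protocol Synopsis plans 840 patients on fasinumab 1 mg Q4W, "840 patients to the naproxen-only group, and 280 patients to the placebo group". The Q8W group is planned at 600.

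**The concern.** DA is a named safety endpoint for Year 1 and Year 2 (Protocol 4.3.1 and 4.3.2). Protocol 1.1 gives it as the reason for the clinical hold on the class and describes it as "a unique clinical form of rapidly progressive arthropathy over and above that seen in the normal progression of osteoarthritis". That description makes a very low count in the smallest arm plausible. A Cox model has no finite estimate when the reference arm has no events. The table would then show a hazard ratio in the millions with limits of about 0 and infinity, or not estimable, whether fasinumab had 3 cases or 200. Someone who looks only at whether the interval includes 1 could take that as reassurance.

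**Working it through.** **Origin of the 280.** The only power figure tied to this arm is for efficacy: effect size 0.46, two-sided alpha 0.025, 30% dropout to week 52, at least 99% power. With 588 and 196 completers, SE = sqrt(1/588 + 1/196) = 0.0825; 0.46/0.0825 = 5.58; 5.58 - 2.24 = 3.34, which gives 99.96%. The stated figure reproduces. The documents give no event count, precision or power for DA.

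**Chance of no placebo case.** This is (1-p)^280, with the placebo DA risk p assumed:

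| p | 0.1% | 0.2% | 0.3% | 0.5% | 1% |
|---|---|---|---|---|---|
| P(no case) | 76% | 57% | 43% | 25% | 6% |

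**The Cox fit with no placebo case.** With about three Q4W patients at risk per placebo patient and x events, all on fasinumab, the partial likelihood is proportional to [3e^b/(3e^b+1)]^x, where b is the log hazard ratio. It rises without limit in b. For large b the standard error is about sqrt(3e^b/x), so b/SE tends to 0. Fits with 3 to 200 events among 840 stopped at a log hazard ratio of 15.5 to 16.5, with SE 445 to 2283 and z 0.007 to 0.037. At 20 events the fitted SE was 882 (formula: sqrt(3 x 5.24 million/20) = 887), so the log-scale limits are 15.5 ± 1.96 x 882, about -1713 to 1744. Every Wald interval contained 1, including at 200 of 840.

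**Methods that still work at zero.**
- Exact conditional: lower limit = [L/(1-L)]/3 with L = 0.025^(1/x). At x = 12, L = 0.735 and the limit is 0.93; at x = 13, L = 0.753 and the limit is 1.02.
- Firth-type, approximated by a likelihood-ratio test with 1/2 added to each count. At x = 11: 2[11.5 ln(0.9583/0.75) + 0.5 ln(0.0417/0.25)] = 3.846, which exceeds 3.841. At x = 10 it is 3.36.

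**Fasinumab cases in 840 needed for the lower limit to pass 1.** The Wald limit uses ln(x/3c) - 1.96 sqrt(1/x + 1/c) for c placebo cases. For example, with x = 23 and c = 1: 2.037 - 2.002 = 0.035, above 0.

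| Placebo cases | Wald | Exact | Firth-type |
|---|---|---|---|
| 0 | never | 13 | 11 |
| 1 | 23 | 19 | 18 |
| 2 | 26 | 25 | 23 |
| 3 | 30 | 30 | 28 |

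**Chance that the 95% CI lies above 1.** Binomial counts were enumerated for 840 versus 280 with equal follow-up. Wald was counted as containing 1 when an arm has no events.

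| Placebo vs fasinumab risk | Wald | Exact | Firth-type |
|---|---|---|---|
| 0.2% vs 2% | 3% | 60% | 68% |
| 0.5% vs 2.5% | 17% | 54% | 61% |
| 1% vs 5% | 85% | 92% | 93% |

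**Error under no effect.** At placebo risks from 0.3% to 1%, the Firth-type interval lay above 1 in at most 1.4% of trials (nominal 2.5% per side). The unpenalised profile-likelihood interval reached 4.8%.

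**The case against.** Several points on the other side stand. The SAP labels the comparison descriptive and sets no rule that the interval must exclude 1. Under Protocol 5.1.8, safety judgement rests on the monitoring committee's view of the totality of evidence. The SAP does not choose Wald limits; it is silent, and a profile-likelihood interval would fit its words and would not fail at zero. No DA rate is given, so how often the problem would arise is assumed, and at 1% placebo risk it is uncommon.

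Four stronger readings are tempting, and the documents do not support them.
- A reader might infer that the plan cannot show joint harm. It can: 20 of 840 against 0 of 280 would be plain in the incidence tables and on the Kaplan-Meier curves, and AA and joint replacement have their own displays.
- A reader might infer that Wald limits also fail with a few placebo cases. With one case the loss is modest (23 needed against 19 exact), and from two on Wald is close to exact (26 against 25, then 30 against 30). What remains is sparse data.
- A reader might apply the concurrent-randomization restriction and compare Q8W with about 200 placebo patients. That restriction belongs to the efficacy sets (SAP 3.1 to 3.3). The safety set in SAP 3.4 does not have it, so about 280 is the planned comparator for Q8W too.
- A reader might credit the whole gain over Wald to penalisation. Most of it comes from any interval that works at zero; exact limits already reach 60% where Firth-type limits reach 68%.

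Profile likelihood alone would also give a finite lower limit at zero, from 7 of 840 cases. Its 4.8% error under no effect, against at most 1.4%, is the reason to prefer the penalised form.

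**Conclusion.** The point holds for one output: the DA hazard ratio versus placebo and its 95% CI. If placebo has no DA case and Wald limits are used, that output is uninformative at any fasinumab count, whereas exact limits pass 1 from 13 of 840 and Firth-type limits from 11. The chance of that situation is 25% to 76% for placebo risks from 0.5% down to 0.1%, and 6% at 1%. The result rests on an assumed DA risk, equal follow-up, the planned 280 patients (the as-treated rules may change that number) and Wald as the default that would be used. The Firth-type figures come from a count approximation, not from full Cox fits. This is a cheap improvement to a descriptive safety analysis; it does not invalidate the safety plan.

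**What to change.** In SAP 5.8.7, state that the DA hazard ratio versus placebo will be estimated by Firth-penalised Cox regression with profile-likelihood 95% limits (PROC PHREG, options FIRTH and RISKLIMITS=PL), and that the same will be done for AA when an arm has no or very few events. Beside it, report the risk difference with a score-type (Miettinen-Nurminen) 95% CI, which is defined when one arm has no events.

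The cost is a short SAP change, two software options and one extra table column, with no new data. The downside is slight shrinkage of the hazard ratio toward 1 when events are few.
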